# **Description of Study Treatments or Exposures/Predictors**

Bottles containing 50mL or 100 mL of 10% Omegaven® will be purchased from International Pharmacy of Hamburg, Germany. Insurance companies will be billed the cost of Omegaven®. If the insurance company does not provide payment, *Healthy* @ *Home, LLC* will cover all drug costs for patients enrolled in this protocol. Omegaven® is manufactured by Fresenius Kabi AG, Bad Homburg, Germany. Omegaven® is formulated as an emulsion from fish oils.

While inpatient, the emulsion for each patient will be provided in its original container for volumes more than 96 ml/day. Doses less than 96 ml/day will be repacked into syringes to allow for administration via syringe pump. If patients are to be discharged home on Omegaven®, all doses will be administered from the original manufacturer's container.

Outpatients will have laboratory data monitored (Table 2) as do inpatients, with values reported to the pediatric gastroenterologists via the Pediatric Nutrition Support Clinic at the Levine Children's Specialty Center. Growth will be tracked weekly. Home health nursing staff and guardians will be educated regarding Omegaven® and administration while the child is still an inpatient prior to discharge. This education will include Omegaven® adverse event monitoring (Table 3) and reporting; administration practices; and information regarding monthly or other mutually agreed upon schedules for clinical evaluation and follow up of the patient by study investigators.

All study materials will be stored securely until the time of administration. The bottles will be stored at room temperature below 30° C (do not freeze). Damaged or suspect drug will be returned unused to Fresenius-Kabi. Containers should be shaken before use.

All supplies for the study protocol will be accompanied by accountability and shipping documents and will be maintained by the Investigator or deputy (e.g. research pharmacist). Information recorded on these accountability and shipping documents will include relevant dates, batch numbers, quantities received or dispensed, to whom dispensed, returned drug and drug lost or damaged.

At the end of the protocol study, all used and unused Omegaven® will be accounted for. If expired, the remaining drug supplies will be destroyed.

#### **Financial Consideration**

A request to charge for Omegaven® has been submitted to the FDA. *Healthy* @ *Home*, *LLC* will assume all costs, in the event that third party payers do not cover the cost of Omegaven®. Study investigators will not receive financial benefit in any form from this research study.

# **Details of Omegaven® Administration**

After baseline labs are obtained (Table II), therapy with Omegaven® will be initiated at a starting dose of 0.5gm/kg/day infused over 12-24 hours. After two days, the dose will be increased to 1 gm/kg/day, the goal dose. Omegaven® will be infused intravenously through either a central or peripheral catheter in conjunction with parenteral nutrition. The same standards of care provided to all patients receiving parenteral nutrition solution will be followed. Laboratory tests will be performed as detailed in Table 2. Growth will be tracked weekly. If additional fat calories are needed, they will be provided via the enteral route.

In the event that a patient is unable to achieve adequate calories parenterally and is unable to tolerate enteral feeds, it may be necessary to evaluate whether or not the patient should continue the study with Omegaven® as monotherapy or resume therapy with conventional fat emulsions at 1 gm/kg in addition to the Omegaven® so that additional parenteral fat calories can be given. The clinical team, in conjunction with the patient's primary physician, will determine if the patient should be removed from the protocol.

As previously mentioned, Omegaven® may be infused in the same manner as conventional fat emulsions through either a central or peripheral line. The emulsion is isotonic. It is compatible with parenteral nutrition solutions and may be co-infused via y-site. Omegaven® may be infused through a 1.2micron inline filter.

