# PHASE II CLINICAL TRIAL HYPOTHESIS

The administration of Omegaven® in place of conventional phytosterol/soybean lipid emulsions will be safely provided to children with intestinal failure (defined as inability to wean from PN, with causes including short bowel syndrome) and PNALD and will reverse or prevent the progression of PN associated cholestasis and will allow the patient to be maintained on adequate PN until they are able to ingest adequate nutrition enterally.

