#### SPECIFIC AIMS/OBJECTIVES

- To determine the impact of Omegaven® on reversal of conjugated hyperbilirubinemia
- To determine the impact of Omegaven® on the prevention of essential fatty acid deficiency
- To determine the impact of Omegaven® administration on serum triglyceride
- To determine the impact of Omegaven® administration on coagulation profiles

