#### **Duration of Therapy**

Patients will complete the study when he/she is completely off PN; develops a contraindication for further use; or the patient/family requests to be removed from the study protocol.

In the event that a patient who has been listed for a liver or liver/intestinal transplant has an organ become available, the participation in this protocol will not preclude them from receiving the transplant. Omegaven® will not be administered post transplant.

In the event that a patient whose hepatic enzymes and serum bilirubin have normalized still requires parenteral fat emulsion after receiving Omegaven® for more than 6 months, their clinical course will be reviewed, and a decision will be made whether to continue the Omegaven® or rechallenge the patient with conventional therapy (Intralipid®).

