# **Definition of Primary and Secondary Outcomes/Endpoints**

The primary outcome is normalization of direct bilirubin to less than 0.4mg/dL by 9 months.

Seconday outcomes include:

- Omegaven® will prevent EFA deficiency as evidenced by normal EFA profiles on monthly evaluations
- The rate of triglyceride levels > 400 mg/dL with Omegaven® will be similar to that seen with PN administered with soy oil IFE (conventional emulsion, i.e., Intralipid®) as evidenced by baseline data and then weekly and monthly evaluations
- PN containing Omegaven® will be safe for patients with respect to the risk of unexpected bleeding/coagulopathies as evidenced by weekly and monthly evaluations

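### Soybean emulsion may be added to Omegaven on study, yet the EFA outcome credits every normal monthly profile to Omegaven

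*Protocol*

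**What the plan says.** The hypothesis is about substitution: "The administration of Omegaven® in place of conventional phytosterol/soybean lipid emulsions". One of the four aims is "To determine the impact of Omegaven® on the prevention of essential fatty acid deficiency", and another is "To determine the impact of Omegaven® administration on serum triglyceride".

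Under Details of Omegaven® Administration, the goal dose is 1 g/kg/day, and the first rule for extra fat keeps soybean lipid out: "If additional fat calories are needed, they will be provided via the enteral route". The next paragraph covers a child who cannot get enough calories parenterally and cannot tolerate enteral feeds. The team then weighs Omegaven monotherapy against a second option, to "resume therapy with conventional fat emulsions at 1 gm/kg in addition to the Omegaven® so that additional parenteral fat calories can be given". The paragraph closes by saying that the clinical team, with the primary physician, "will determine if the patient should be removed from the protocol". Removal is therefore possible but not required.

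Neither list of exits names added soybean lipid. Duration of Therapy says "Patients will complete the study when he/she is completely off PN; develops a contraindication for further use", or when the family asks to leave. The withdrawal reasons under Adverse Event Criteria and Reporting Procedures are toxicity, family request, transplant, the investigator's judgement of the patient's best interest, and loss to follow-up.

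The EFA outcome, under Definition of Primary and Secondary Outcomes/Endpoints, reads: "Omegaven® will prevent EFA deficiency as evidenced by normal EFA profiles on monthly evaluations". It has no condition on concurrent soybean emulsion. The triglyceride outcome compares the rate above 400 mg/dL on Omegaven with that on soy oil emulsion, again without such a condition.

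**The concern.** The treatment rule and the outcome definition do not fit together. The rule allows a child on study to receive the lipid that Omegaven is meant to replace. The outcome then reads that child's normal EFA profile as evidence for Omegaven.

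This touches the question that the protocol itself treats as contested. The section on preliminary studies notes the long-held fear that removing omega-6 fat from parenteral nutrition would cause EFA deficiency, and it answers with experience of Omegaven used alone. A normal profile in a child also receiving soybean oil does not bear on that question. Pooling such profiles can only make prevention of deficiency look better than Omegaven alone achieves.

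Triglycerides raise a related but different issue. On the mixture the parenteral fat dose doubles and includes the comparator lipid, so these values do not give a clean comparison of Omegaven with soy oil emulsion. Any bias would probably run against Omegaven.

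**Working it through.** The protocol gives no figure for this point, so there is none to reproduce.

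**Inputs**
- Omegaven goal dose 1 g/kg/day, and soybean add-on 1 g/kg (Details of Omegaven® Administration). The add-on is taken as per day, with Omegaven staying at its goal dose. A lower Omegaven dose would raise the soybean share.
- Conventional emulsion is taken as Intralipid, the example given in the outcomes section.
- Linoleic acid (Table 1): Intralipid 50% of fat; Omegaven 0.1-0.7. The unit of the Omegaven entry is unclear (g per 100 mL or % of fat), so both readings are used.
- Planned enrolment 20-25 (Recruitment Methods).
- Assumed, because the protocol gives no frequency: one child on the mixture from month 3 to month 9, all children sampled monthly for 9 months. Nine months is the horizon of the primary outcome; the EFA outcome has no time limit of its own.

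**Fat and linoleic acid per kg per day**
- Parenteral fat: 1 + 1 = 2 g/kg, double the monotherapy dose.
- Linoleic acid from soybean emulsion: 1 × 0.50 = 0.5 g/kg.
- Linoleic acid from Omegaven: a 10% emulsion at 1 g/kg is 10 mL/kg. That gives 0.01-0.07 g/kg if Table 1 is in g per 100 mL, or 0.001-0.007 g/kg if it is % of fat.

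| Linoleic acid from Omegaven (g/kg) | Total on mixture (g/kg) | Mixture ÷ monotherapy | Soybean share |
|---|---|---|---|
| 0.07 | 0.57 | 8.1 | 87.7% |
| 0.01 | 0.51 | 51 | 98.0% |
| 0.007 | 0.507 | 72 | 98.6% |
| 0.001 | 0.501 | 501 | 99.8% |

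The least extreme case is an 8-fold rise with about 88% from soybean oil, so the unclear unit does not change the conclusion.

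**Weight in the EFA outcome (assumed scenario)**
- Per monthly value: 6/(25 × 9) = 6/225 = 2.7%; 6/(20 × 9) = 6/180 = 3.3%.
- Per child, if one child's profiles are normal only because of the added soybean lipid: 1/25 = 4 points; 1/20 = 5 points.

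**Sensitivity to frequency**

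Suppose the true deficiency rate on monotherapy is 10% per child and mixture children show none (both assumed). The pooled rate is (1 − m) × 10%, where m is the share of children on the mixture. With 20 children:
- 1 on the mixture (m = 5%): 9.5%
- 2 (10%): 9.0%
- 4 (20%): 8.0%
- 6 (30%): 7.0%

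The distortion is slight if the fallback is rare and becomes noticeable only if it is common.

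**The case against.** The strongest objection is that handling of values after added therapy belongs in the statistical analysis plan, which is not at hand; the Data Analysis Plan section leaves the specific analysis to the statistician. This stands in part, and missing analysis detail alone would be no finding. But the protocol itself fixes both the treatment rule and the outcome wording, and the two do not fit. Dates and dose also have to be captured as the trial runs.

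Second, removal can be read as part of the same evaluation, and withdrawal in the patient's best interest is already provided for. So the text does not show that a child on the mixture will stay on study. It shows only that the child may.

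Third, the feeding history under Data Collection Methods already covers parenteral intake, so much of what is needed may be recorded anyway. That is true, and it is why the fix is cheap.

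Two stronger readings are tempting, and the documents do not support them:
- A reader might count EFA values on the weekly laboratory schedule, which a child with persistent cholestasis would stay on, and obtain a larger mixture share. The outcome is defined on monthly evaluations, so that count does not apply.
- A reader might infer that triglycerides above 400 mg/dL on the mixture should leave the Omegaven rate. High triglycerides are themselves a safety signal (Dose Modification; Overdose), Omegaven is still running, and dropping them would select on an event after baseline. They should stay in.

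**Conclusion.** The point holds as a minor one. The protocol permits soybean emulsion on top of Omegaven in a child who may remain on study, and its EFA outcome does not separate those profiles. On the mixture about 88% or more of parenteral linoleic acid is from soybean oil, so those profiles cannot support the claim about Omegaven as a replacement.

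The linoleic acid figures rest on Table 1 and the stated doses. The 2.7-3.3% of monthly values and 4-5 points per child rest on an assumed single child. The real frequency is unknown and may be low, because the fallback needs both parenteral calories and enteral feeding to fail.

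It would be too strong to infer that the EFA aim is defeated or that the fallback is wrong. The fallback is a reasonable clinical safeguard, the outcome is secondary, and the study states that it does not aim to prove statistical significance.

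**What to change.** Leave the clinical decision with the team, and make these changes:

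1. **Data collection.** In the feeding history, record start date, stop date and dose of any parenteral soybean emulsion given after the first Omegaven infusion.
2. **EFA outcome.** Base the conclusion on prevention of deficiency on monthly profiles drawn on Omegaven without concurrent soybean emulsion, and show the mixture profiles alongside.
3. **Triglyceride outcome.** Keep all values in the overall Omegaven rate. Report the monotherapy-only rate beside it for the comparison with soy oil emulsion.
4. **Coagulation and bleeding.** Keep all data in the Omegaven safety results, flagged where drawn on the mixture.

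The cost is three fields on an existing form and a few sentences in the outcomes section. The downsides should be stated:
- The main EFA summary has slightly fewer values.
- There is some selection, because children who reach the fallback are likely to be sicker. Reporting both sets keeps this visible.
- Profiles drawn soon after soybean emulsion stops may carry over its effect. The stop date shows which these are.
- Enteral fat, which the protocol allows for any child needing more fat calories, remains a separate source of linoleic acid that this change does not remove.

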#### **Dose Modification**

Hypertriglyceridemia:

If hypertriglyceridemia develops, defined as serum triglyceride levels > 200 mg/dL, the following will be considered prior to reducing the dose:

- a) If the level was obtained while the patient was receiving a continuous 24- hour infusion of Omegaven®, the total dose should be infused over 20 hours, and a repeat serum triglyceride level obtained prior to resuming the infusion 4 hours later.
- b) Other sources of hypertriglyceridemia should be considered and addressed (drugs, renal disease)

If necessary, if the triglycerides continue to remain high despite the aforementioned interventions, a dosage reduction of 25% will be considered.

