#### Overdose:

In the event of an overdose of Omegaven®, there is a risk of developing fat overload syndrome that may occur when the triglyceride level rises >200 mg/dL acutely as a result of too rapid a rate of infusion, or chronically at high infusion rates in associated with a change in the patient's clinical condition (e.g., renal dysfunction, sepsis). In such cases, the infusion should be stopped or, if necessary, continued at a reduced dose.

Metabolic acidosis has occurred in patients receiving Omegaven® at excessive doses without simultaneous administration of dextrose.

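### Three sections of the protocol attach different first actions to the same triglyceride value (above 200 mg/dL)

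*Protocol*

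**What the plan says.** Three places in the protocol act on a triglyceride level above 200 mg/dL.

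- **Dose Modification (Hypertriglyceridemia).** The section opens: "If hypertriglyceridemia develops, defined as serum triglyceride levels > 200 mg/dL, the following will be considered prior to reducing the dose". Step (a) applies "If the level was obtained while the patient was receiving a continuous 24- hour infusion of Omegaven". In that case "the total dose should be infused over 20 hours", with "a repeat serum triglyceride level obtained prior to resuming the infusion 4 hours later". Step (b) looks for other sources, drugs and renal disease being the examples. Only then, "if the triglycerides continue to remain high despite the aforementioned interventions, a dosage reduction of 25% will be considered".
- **Data and Safety Monitoring Plan.** This section lists triglycerides above 200 mg/dL among the findings at which the dose is to be reduced. It names no preceding step, sets no further condition, and does not refer back to Dose Modification.
- **Overdose (under Risks and Discomforts).** It begins: "In the event of an overdose of Omegaven®, there is a risk of developing fat overload syndrome that may occur when the triglyceride level rises" above 200 mg/dL. It gives two routes. One is acute: "when the triglyceride level rises >200 mg/dL acutely as a result of too rapid a rate of infusion". The other is chronic: high infusion rates together with a change in the patient's condition, such as renal dysfunction or sepsis. The action is: "In such cases, the infusion should be stopped or, if necessary, continued at a reduced dose".

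**The concern.** The trigger is the same number in all three places, but the first action differs. Dose Modification holds the daily dose and, in step (a), compresses it into fewer hours. The Data and Safety Monitoring Plan cuts the dose. The Overdose section stops the infusion or lowers the dose, and one cause it names is the quantity that step (a) increases, the hourly rate.

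Staff who follow the protocol faithfully could treat the same child differently according to the page they open. That affects patient safety in a population of sick infants and children. It also makes the administered dose, and adherence to the protocol, hard to interpret in a small uncontrolled study of 20 to 25 patients.

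**Working it through.** The protocol states no hourly rate for step (a), so there is no figure of its own to reproduce. The check is arithmetic on the rate, followed by a comparison of the sections.

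**Inputs**
- Threshold: above 200 mg/dL (Dose Modification; Data and Safety Monitoring Plan; Overdose).
- Infusion time before and after step (a): 24 h and 20 h, same total dose (Dose Modification).
- Starting dose 0.5 g/kg/day over 12 to 24 h; goal dose 1 g/kg/day (Details of Omegaven Administration).
- Strength: 10%, that is 0.1 g/mL (Description of Study Treatments).

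**Change in hourly rate**

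Rate = D / h for daily dose D over h hours. Relative change = (D/20) / (D/24) − 1 = 24/20 − 1 = 0.20, at any dose.

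- Goal dose: 1 / 0.1 = 10 mL/kg/day. Over 24 h, 10/24 = 0.417 mL/kg/h; over 20 h, 10/20 = 0.500 mL/kg/h.
- Starting dose: 0.5 / 0.1 = 5 mL/kg/day. Over 24 h, 5/24 = 0.208 mL/kg/h; over 20 h, 5/20 = 0.250 mL/kg/h.

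**If the 25% reduction follows (goal dose)**

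Reduced volume: 0.75 × 10 = 7.5 mL/kg/day.

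- Over 24 h: 7.5/24 = 0.3125 mL/kg/h, which is 25% below 0.417.
- Still over 20 h: 7.5/20 = 0.375 mL/kg/h, which is 10% below 0.417 (0.375/0.4167 = 0.90).

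The protocol does not say which infusion time goes with the reduced dose, so its effect on the rate is open.

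**One child, three sections**

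Take a level of 210 mg/dL drawn on a continuous 24-hour infusion at the goal dose.

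| Section | Daily dose at first | Hourly rate at first |
|---|---|---|
| Dose Modification, step (a) | unchanged | up 20% while running, then 4 h off and a re-test |
| Data and Safety Monitoring Plan | reduced, amount not stated | not stated |
| Overdose, if it applies | stopped, or reduced | zero, or not stated |

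**Does the Overdose section apply to this child?** The only number in that section is the 200 mg/dL already used in Dose Modification. No dose, rate or clinical sign is given to separate an overdose from an ordinary raised value. The two sections also overlap: kidney disease is a source to look into before any reduction under Dose Modification, and an example of the chronic route under Overdose.

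**The case against.** The strongest reply is that the sections address different situations. The Overdose text is conditional: it starts from an overdose and the risk of fat overload syndrome, and its action refers back to that. Dose Modification deals with an abnormal laboratory value at the protocol dose. Step (a) is a single sentence that opens a 4-hour break so that a level drawn during infusion can be repeated off infusion. On that reading the faster rate is a by-product of the break, and a reduction still follows for consideration if levels stay high. The adverse event section also points back to the earlier dose-modification rules, which suggests that those govern. The Data and Safety Monitoring Plan sentence might then be only a loose summary.

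Much of this stands, and it rules out some stronger readings:

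- A reader might infer that the protocol blames every level above 200 mg/dL on a 24-hour infusion on too rapid a rate. It does not. Rate is one of two routes, and 24 hours is the slowest schedule in the 12 to 24 hour range given with the starting dose.
- A reader might infer that step (a) directly reverses the Overdose instruction. That holds only if the child counts as an overdose case, which the protocol leaves undefined.
- A reader might infer that step (a) is shown to cause harm, or that the re-test hides a higher level during the faster infusion. No section says that 0.500 mL/kg/h is too rapid. It equals, and does not exceed, the maximum of 0.5 mL/kg/h reported from earlier adult use. That is context only and does not establish safety. Masking is possible but not demonstrated.

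The reply does not remove the conflict with the Data and Safety Monitoring Plan, which needs no overdose condition: a reduction that is required and a reduction that is considered only after other steps are different rules. Nor does it supply the missing boundary for the Overdose text.

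**Conclusion.** The inconsistency is real and should be corrected. At one threshold, above 200 mg/dL, the protocol gives different first actions. The unconditional conflict is between Dose Modification (other steps first, 25% reduction only considered) and the Data and Safety Monitoring Plan (reduction required). The conflict with the Overdose section is conditional, and the protocol gives no way to tell when the condition is met.

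The rate change in step (a) is exactly 20% at any fixed dose. The mL/kg/h figures assume the 10% emulsion and the stated doses. The conclusion concerns consistency; it does not say that any of the rates or rules is clinically wrong.

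**What to change.** The sponsor and investigator should reconcile Dose Modification, the Data and Safety Monitoring Plan and Overdose into one instruction for triglycerides above 200 mg/dL. It should state:

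1. what happens to the total daily dose, and whether that action is required or considered;
2. what happens to the hourly rate, including the infusion time that goes with any reduced dose;
3. what marks a case as one for the Overdose instruction.

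The other sections should then refer to that instruction and not restate it. Which rule to adopt is for the clinical team.

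Optionally, record on the laboratory form whether each triglyceride sample was drawn during infusion or after a break. Step (a) mixes the two kinds of value, although no effect on the secondary outcome, which uses levels above 400 mg/dL, has been shown.

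The cost is a protocol wording change with the usual approvals and, if the option is taken, one extra field.
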